12.1.4.2 Adverse Events of Special Interest for the Adjuvants

12.1.4.2.1 Potential Immune-Mediated Diseases and Other AESI

Potential immune-mediated diseases (pIMDs) are a subset of AEs that include autoimmune diseases and other inflammatory and/or neurologic disorders of interest which may or may not have an autoimmune aetiology. Adverse events that need to be recorded and reported as pIMDs include those listed in Appendix 3.

However, the Investigator will exercise their medical and scientific judgement in deciding whether other diseases have an autoimmune origin (that is pathophysiology involving systemic or organ-specific pathogenic autoantibodies) and should also be recorded as a pIMD.

When there is enough evidence to make any of the diagnoses mentioned in Appendix 3, the AE must be reported as a pIMD. Symptoms, signs or conditions which might (or might not) represent the above diagnoses, should be recorded and reported as AEs but not as pIMDs until the final or definitive diagnosis has been determined, and alternative diagnoses have been

eliminated or shown to be less likely.

In order to facilitate the documentation of pIMDs in the eCRF, a pIMD standard questionnaire and a list of preferred terms (PTs) and PT codes corresponding to the above diagnoses will be available to Investigators at study start.

Once a pIMD is diagnosed (serious or non-serious) in a study subject, the Investigator must complete, date and sign an Serious Adverse Events Report.

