7.1.3.1.3 Adverse Events of Special Interest (AESI)

7.1.3.1.3.1 Vaccine Associated Enhanced Disease (VAED)

Safety signal of VAED after exposure to the CoVLP formulation will be closely monitored and assessed by retrieving data for this AESI as follows: AEs within the system organ class (SOC): immune system disorders and high level group term (HLGT): lower respiratory tract disorders (excluding obstruction and infection), cardiac disorders, signs and symptoms not elsewhere classified, vascular disorders, heart failures, arteriosclerosis, stenosis, vascular insufficiency and necrosis, cardiac arrhythmias, myocardial disorders, and vascular hemorrhagic disorders. High level term (HLT): renal failure and impairment and preferred term (PT): pericarditis, coagulopathy, deep vein thrombosis, pulmonary embolism, cerebrovascular accidents, peripheral ischemia, liver injury, Guillain-Barre syndrome, anosmia, ageusia, encephalitis, chilblains, vasculitis, erythema multiforme that require inpatient hospitalization (≥ 24 hours) and have laboratory confirmed SARS-CoV-2 infection will be monitored for assessment of any

potential case of VAED. As this list can be updated during the study, any further changes to the AESI terms will be updated in the Signal Management Plan (SMP).

VAED list is attached in the Appendix.

7.1.3.1.3.2 Hypersensitivity Reactions (Anaphylaxis and Severe Allergic Reactions)

All reported events will also be monitored for related hypersensitivity reactions after exposure to the CoVLP formulation. Hypersensitivity will be identified using SMQ broad and narrow terms.

Hypersensitivity reaction list is attached in the Appendix.

7.1.3.1.3.3 Potential Immune-Mediated Diseases (pIMD)

Potential immune-mediated diseases (pIMDs) are a subset of AEs associated to the adjuvant that include autoimmune diseases and other inflammatory and/or neurologic disorders of interest which may or may not have an autoimmune aetiology. pIMDs will be identified using SMQ terms.

pIMD list is attached in the Appendix.

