APPENDIX 4 PIMD

PT
Acute cutaneous lupus erythematosus
Acute disseminated encephalomyelitis
Acute febrile neutrophilic dermatosis
Acute flaccid myelitis
Acute haemorrhagic leukoencephalitis
Acute haemorrhagic oedema of infancy
Acute macular neuroretinopathy
Acute motor axonal neuropathy
Acute motor-sensory axonal neuropathy
Acute necrotising myelitis
Addison's disease
Administration site vasculitis
Alopecia areata
Alveolar proteinosis
Ankylosing spondylitis
Anti-glomerular basement membrane disease
Anti-LRP2 nephropathy
Anti-myelin-associated glycoprotein associated polyneuropathy
Anti-neutrophil cytoplasmic antibody positive vasculitis
Antiphospholipid syndrome
Anti-RNA polymerase III antibody increased
Anti-RNA polymerase III antibody positive
Antisynthetase syndrome
Aortitis
Application site vasculitis
Arteritis
Arteritis coronary
Arthritis enteropathic
Arthritis reactive
Atrophic thyroiditis
Autoimmune anaemia
Autoimmune aplastic anaemia
Autoimmune arthritis
Autoimmune blistering disease
Autoimmune cholangitis
Autoimmune colitis
Autoimmune demyelinating disease

Autoimmune dermatitis
Autoimmune disorder
Autoimmune encephalopathy
Autoimmune endocrine disorder
Autoimmune enteropathy
Autoimmune eye disorder
Autoimmune haemolytic anaemia
Autoimmune heparin-induced thrombocytopenia
Autoimmune hepatitis
Autoimmune hyperlipidaemia
Autoimmune hypothyroidism
Autoimmune inner ear disease
Autoimmune lung disease
Autoimmune lymphoproliferative syndrome
Autoimmune myocarditis
Autoimmune myositis
Autoimmune nephritis
Autoimmune neuropathy
Autoimmune neutropenia
Autoimmune pancreatitis
Autoimmune pancytopenia
Autoimmune pericarditis
Autoimmune retinopathy
Autoimmune thyroid disorder
Autoimmune thyroiditis
Autoimmune uveitis
Autoinflammatory disease
Axial spondyloarthritis
Axonal and demyelinating polyneuropathy
Axonal neuropathy
Basedow's disease
Behcet's syndrome
Bell's palsy
Bickerstaff's encephalitis
Birdshot chorioretinopathy
Brachial plexopathy
Bulbar palsy
C1q nephropathy
Capillaritis
Capillary leak syndrome
Caplan's syndrome

Cardiac sarcoidosis
Central nervous system lupus
Central nervous system vasculitis
Cerebral arteritis
Cholangitis sclerosing
Chronic autoimmune glomerulonephritis
Chronic cutaneous lupus erythematosus
Chronic inflammatory demyelinating polyradiculoneuropathy
Chronic lymphocytic inflammation with pontine perivascular enhancement responsive to steroids
Chronic pigmented purpura
Clinically isolated syndrome
Coeliac disease
Cogan's syndrome

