Cold type haemolytic anaemia
Colitis erosive
Colitis microscopic
Colitis ulcerative
Collagen-vascular disease
Concentric sclerosis
Coombs positive haemolytic anaemia
Cranial nerve disorder
Cranial nerve palsies multiple
Cranial nerve paralysis
CREST syndrome
Crohn's disease
Cutaneous lupus erythematosus
Cutaneous sarcoidosis
Cutaneous vasculitis
Demyelinating polyneuropathy
Demyelination
Dermatitis bullous
Dermatitis herpetiformis
Dermatomyositis
Diffuse vasculitis
Encephalitis allergic
Encephalitis autoimmune
Encephalitis brain stem
Encephalitis haemorrhagic
Encephalitis periaxialis diffusa

Encephalitis post immunisation
Encephalitis toxic
Encephalomyelitis
Endocrine ophthalmopathy
Enteropathic spondylitis
Eosinophilic fasciitis
Eosinophilic granulomatosis with polyangiitis
Erythema induratum
Erythema multiforme
Erythema nodosum
Evans syndrome
Expanded disability status scale score decreased
Expanded disability status scale score increased
Facial paralysis
Facial paresis
Felty's syndrome
Fibrillary glomerulonephritis
Fulminant type 1 diabetes mellitus
Giant cell arteritis
Giant cell myocarditis
Glomerulonephritis membranoproliferative
Glomerulonephritis membranous
Glomerulonephritis rapidly progressive
Glossopharyngeal nerve paralysis
Goodpasture's syndrome
Gout
Gouty arthritis
Gouty tophus
Granulomatosis with polyangiitis
Granulomatous dermatitis
Guillain-Barre syndrome
Haemorrhagic occlusive retinal vasculitis
Haemorrhagic vasculitis
Hashimoto's encephalopathy
Hashitoxicosis
Henoch-Schonlein purpura
Henoch-Schonlein purpura nephritis
Hypersensitivity vasculitis
Hypoglossal nerve paralysis
Hypoglossal nerve paresis
Idiopathic inflammatory myopathy

Idiopathic interstitial pneumonia
Idiopathic pulmonary fibrosis
IgA nephropathy
IgM nephropathy
IIIrd nerve paralysis
IIIrd nerve paresis
Immune thrombocytopenia
Immune-mediated adrenal insufficiency
Immune-mediated adverse reaction
Immune-mediated arthritis
Immune-mediated cholangitis
Immune-mediated cholestasis
Immune-mediated cystitis
Immune-mediated cytopenia
Immune-mediated dermatitis
Immune-mediated encephalitis
Immune-mediated encephalopathy
Immune-mediated endocrinopathy
Immune-mediated enterocolitis
Immune-mediated gastritis
Immune-mediated hepatic disorder
Immune-mediated hepatitis
Immune-mediated hyperthyroidism
Immune-mediated hypophysitis
Immune-mediated hypothyroidism
Immune-mediated lung disease
Immune-mediated myocarditis
Immune-mediated myositis
Immune-mediated nephritis

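### The SAP counts potential immune-mediated diseases (pIMDs) from a term list alone, so an investigator-reported pIMD coded to an unlisted term would be left out of the pIMD row (minor)

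*SAP*

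**What the plan says.** **Protocol 12.1.4.2.1** treats pIMD as a category that the investigator assigns on the basis of a diagnosis.

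- The list is open-ended: "Adverse events that need to be recorded and reported as pIMDs include those listed in Appendix 3".
- Beyond the list, "the Investigator will exercise their medical and scientific judgement in deciding whether other diseases have an autoimmune origin"; a disease so judged is one that the investigator has found autoimmune "and should also be recorded as a pIMD".
- A diagnosis is needed first. Signs, symptoms or conditions that might represent a listed diagnosis "should be recorded and reported as AEs but not as pIMDs until the final or definitive diagnosis has been determined".
- Investigators receive a pIMD questionnaire and a list of preferred terms (PTs). A diagnosed pIMD, serious or not, requires a signed SAE report. Protocol 12.1.6 requires AESIs to be reported within 24 hours.

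**SAP 7.1.3.1.3.3** gives the analysis rule: "pIMDs will be identified using SMQ terms", followed by "pIMD list is attached in the Appendix". It mentions neither the investigator's designation nor a diagnosis requirement.

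**Use of the count.** pIMDs are one of three AESI classes in primary safety endpoint 4 (SAP 2.2.1). SAP 8.3.2 gives them their own entry in the overall safety summary, for each 21-day vaccination period and up to end of study. SAP Section 10, on changes from the protocol, does not mention the counting rule.

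**The concern.** The two documents do not describe the same set of events. The protocol collects pIMDs through the investigator, with a list as an aid and room to go beyond it. The SAP counts them by matching coded terms. A disease that the investigator diagnosed, judged autoimmune and reported as a pIMD is counted only if its PT is in Appendix 4.

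A mismatch would be visible and awkward. The safety files would hold a signed pIMD report while the AESI table showed none. Protocol 13.3 also lists a pIMD diagnosis among the contraindications to the second injection, so the same subject could be recorded as not receiving it for a pIMD that the table does not contain. pIMD is the AESI class that both documents tie to the adjuvant, so whether the row reads zero will be noticed.

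There is a smaller mismatch in the other direction. Appendix 4 contains a few terms that are not diagnoses, and under the SAP rule these would count without one.

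**Working it through.** The documents state no figure on this point, and the sample size has no power basis (SAP 3.4), so there is no plan figure to reproduce. The check is a comparison of text, followed by an illustration of size.

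**1. Routes into the count**

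| Event | Protocol 12.1.4.2.1 | SAP 7.1.3.1.3.3 |
|---|---|---|
| Diagnosed disease, PT listed | pIMD | counted |
| Diagnosed disease judged autoimmune and reported as pIMD, PT not listed | pIMD | not counted |
| Listed term that is a test result or score, no diagnosis | AE, not yet a pIMD | counted if reported as an AE |

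**2. Can the second row occur?** The unqualified terms *Encephalitis*, *Glomerulonephritis*, *Myositis* and *Thyroiditis* are not in Appendix 4. Qualified forms of all four are, for example *Encephalitis autoimmune*, *Chronic autoimmune glomerulonephritis*, *Autoimmune myositis* and *Autoimmune thyroiditis*. The catch-alls *Autoimmune disorder* and *Immune-mediated adverse reaction* are there too. So the row needs a disease judged autoimmune but reported in words that code to a plain or otherwise unlisted PT. The catch-alls narrow this gap but do not close it, because a specific diagnosis is coded to its own term.

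**3. Can the third row occur?** Appendix 4 includes "Anti-RNA polymerase III antibody positive" and "Expanded disability status scale score increased", lupus activity-index terms, and *Multiple sclerosis relapse prophylaxis*. None of these tests or scores is scheduled (Table 1 in both documents; SAP 8.3.3), and a hit requires the finding to be reported as an AE.

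**4. Where does a missed event go?** It stays among the unsolicited AEs (collected to Day 49), among SAEs or MAAEs if it qualifies, and in the listings, since SAP 8.3 lists all safety data. It leaves the pIMD row. It also leaves the AESI total unless another AESI definition captures it. For instance, the VAED paragraph of the SAP names encephalitis, but only with hospitalization and laboratory-confirmed infection.

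**5. Size (assumed counts; planned n = 100 and 25, SAP 3.2).** Exact Clopper-Pearson 95% limits are Beta(0.025; x, n−x+1) and Beta(0.975; x+1, n−x). The lower limit is 0 when x = 0.

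| Group | Investigator-reported case counted | Same case left out |
|---|---|---|
| MT-2766 3.75 µg | 1/100 = 1.0% (0.03 to 5.45%) | 0/100 = 0% (0 to 3.62%) |
| Placebo | 1/25 = 4.0% (0.10 to 20.35%) | 0/25 = 0% (0 to 13.72%) |

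One case is 1/100 = 1.0 percentage point in the vaccine group and 1/25 = 4.0 points in placebo.

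**6. How few cases to expect.** The documents give no pIMD rate, so the following rates are assumptions. P(at least one in 100) = 1 − (1 − p)^100:

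- p = 0.1%: 1 − 0.999^100 = 9.5%
- p = 0.5%: 1 − 0.995^100 = 39.4%
- p = 1%: 1 − 0.99^100 = 63.4%
- p = 2%: 1 − 0.98^100 = 86.7%

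At 0.1% to 1% the expected number is 100p = 0.1 to 1 case. These are chances of any pIMD. The chance of one coded to an unlisted term is smaller, by a factor that the documents do not allow one to estimate.

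**The case against.** The case for leaving the SAP alone has several parts, and much of it stands.

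- **The SAP does not exclude investigator-reported pIMDs.** That is so: the exclusion follows from one route being named and no other. A reader might infer that the SAP overrides the protocol's definition, because SAP Section 1 gives it precedence. The documents do not support this. That clause covers the protocol's statistical analysis text, and 12.1.4.2.1 is a recording and reporting rule. The reports remain required; only their use in the table is unspecified.
- **A PT list is part of the protocol's own approach.** Also so, but there it helps investigators document pIMDs and does not limit what counts. Protocol Appendix 3 is not in the text available for this review. It therefore cannot be said that any protocol-listed diagnosis is missing from SAP Appendix 4.
- **The event is not lost.** Correct. A reader might infer that it disappears from the safety report. It does not: only the pIMD row and, normally, the AESI total differ.
- **The list can be updated.** The SAP sends changes in AESI terms to the Signal Management Plan. The sentence sits in the VAED paragraph, and even read broadly it changes terms. It does not create a route for the investigator's designation.
- **False hits are close to hypothetical.** This stands. No such tests are scheduled, and exclusion criterion 3 names multiple sclerosis and lupus, subject to investigator discretion. Marking the terms in the listing is enough.
- **No conclusion turns on it.** A reader might infer that one case changes the trial's conclusion. The endpoint is descriptive, with no test or threshold, and the intervals for 0/100 and 1/100 overlap heavily.

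**Conclusion.** The point holds as a minor one. Followed as written, the SAP would leave an investigator-reported pIMD with an unlisted PT out of a row that feeds primary safety endpoint 4. The probability is low given the breadth of Appendix 4. The effect is one case at a time, 1.0 point in the vaccine group or 4.0 points in placebo, and it can decide whether the table shows any pIMD.

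This rests on three things: reading the single named route as the one that would be programmed; the planned group sizes as denominators; and assumed case counts and rates, since the documents give none. No test, significance level or sample size is affected.

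**What to change.** In SAP 7.1.3.1.3.3, define the pIMD row as the union of:

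1. all events that the investigator reported as a pIMD (pIMD questionnaire, or SAE/AESI report); and
2. all Appendix 4 term hits.

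Show the two sources separately in the table or the listing. In the listing, mark hits on terms that are not diagnoses (antibody results, disability or activity scores, *Multiple sclerosis relapse prophylaxis*) as not meeting the protocol's diagnosis requirement unless a diagnosis was reported. Record the rule in SAP Section 10.

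If hits are reviewed medically, use a reviewer who is not given the allocation. A review timed before unblinding is not a workable condition here. Key open follows the Day 42 lock (Protocol 5.5), and Section 10 of this final-analysis SAP already reports that the study was discontinued.

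The cost is a few sentences and one derived variable. The investigator reports are already required under Protocol 12.1.4.2.1 and 12.1.6, so no new data are needed.

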7.1.3.2 Laboratory Tests

(1) Laboratory values below the limit of quantification

1/2 LLOQ (lower limit of quantification) will be used for BLQ (below the limit of quantification) data in summary statistics.

7.2 Analysis Visit Definitions

The date of the first vaccination is defined as Day 0.

For the Day 21 visits, a window of +/- 2 days will be applied to sample collection data. For the Day 24 visits, a time window is +/- 1 days from the date of vaccination 2 + 3. For the Day 42 visits, a time window is +/- 2 days from the date of vaccination 2 + 21. For the Day 128 visits, a time window is +/- 14 days from the date of vaccination 2 + 107. For the Day 201 visits, a time window is +/- 14 days from the date of vaccination 2 + 180. Subjects who have blood samples for immunogenicity taken outside of the time window for blood sample collection are to be excluded from the IPP set for the specific visit.

Unless otherwise specified, baseline will be the last observed value of the parameter of interest prior to the first vaccination. For post-baseline visit, if there are multiple data in a window, the later data will be used.

7.3 Data Handling Convention for Missing Data

Concomitant medication:

There is no imputation for completely missing dates.

Missing or partial concomitant medication start date:

- If only DAY is missing, use the first day of the month.
- If DAY and Month are both missing, use the first day of the year.

Missing or partial concomitant medication stop date:

- If only DAY is missing, use the last day of the month.
- If DAY and Month are both missing, use the last day of the year.
- If DAY, Month and year are all missing, assign ‘continuing’ status to stop date.

Immunogenicity:

Missing immunogenicity data will be retained as missing.

Adverse events:

There is no imputation for completely missing dates.

Missing or partial AE date:

No imputation of AE partial/missing start/end dates or times will be performed. In case of missing or incomplete AE onset date/time, the AE will be included in the analysis unless the incomplete AE onset date/time information unequivocally indicates that the AE started prior to Day 0.

If an AE allocation to a reporting cannot be unequivocally ascertained due to partial/missing date, the AE will be allocated to all relevant periods.

Missing relatedness and intensity of AEs will not be imputed and will be presented as “Missing”.

Other safety:

For safety summaries, only observed data will be used. Unless otherwise specified, missing safety data will not be imputed.

8 STATISTICAL METHODOLOGY

8.1 Study Subjects

8.1.1 Subject Disposition and Analysis Population

Subject disposition will be presented for all the subjects.

Analysis populations will be summarized on the randomized population.

Randomization details will be listed on the randomized population. Subject disposition will be listed on the randomized population.

Analysis populations will be listed on the randomized population.

8.1.2 Demographic and Other Baseline Characteristics

The following demographic and other baseline characteristics will be used.

	category	descriptive
Gender	Male, Female	
Age(years)	< 65 >= 65	Yes
Height(cm)		Yes
Weight(kg)		Yes
BMI(kg/m ²)		Yes
Race	Japanese, Other	
Ethnicity	Hispanic or Latino, Not Hispanic or Latino	
Baseline SARS-CoV-2 antibody test	Positive, Negative	
Baseline SARS-CoV-2 PCR test	Positive, Negative	
Significant comorbidities	Yes, No	

Demographic and other baseline characteristics will be summarized on the Immunogenicity ITT set, Immunogenicity PP set and the SAS.

Other baseline characteristics will be listed on the randomized population.

8.1.3 Medical History

Medical history will be summarized on the SAS.

Medical history will be listed on the randomized population.

8.1.4 Prior or Concomitant Medications

Prior medication and concomitant medication (Up to Day 42 and after Day 43) will be summarized separately on the SAS.

Prior and concomitant medication will be listed on the SAS.

8.2 Immunogenicity Assessments

All immunogenicity data will be listed.

The following primary immunogenicity and safety endpoints are for Group 1 and Group 2.

8.2.1 Primary Immunogenicity Endpoint

8.2.1.1 Nab response against the SARS-CoV-2 virus

The following analyses for the Nab assay will be performed:

- GMT (Day 0, Day 21, and Day 42): The point estimates and the corresponding two-sided 95 % CI by treatment group will be calculated.
- SC rate (Day 21, and Day 42): The point estimates and the corresponding two-sided 95 % CI for subjects achieving SC by treatment group will be calculated.
- GMFR: the geometric mean of the ratio of GMTs (Day 21/Day 0 and Day 42/Day 0) will be calculated.

GMT will be compared between treatment groups using the analysis of variance (ANOVA) model.

<Sample SAS code>

For SC rate, Fisher's exact tests will be used to compare between the treatment groups, along with exact Clopper-Pearson 95% CI.

GMFR will be compared using the ANCOVA model. The GMFR will be derived by using ANCOVA to model the difference in the log of the titer values between Day 21 and Day 0 and

between Day 42 and Day 0, with treatment group as main effect and log-transformed baseline titer as covariate.

The reverse cumulative distribution (RCD) curve (plot % of population against the antibody titres) will be plotted and scatter plot will be created.

8.2.1.2 Specific Th1 CMI response against the SARS-CoV-2 virus measured by IFN- γ ELISpot

The specific Th1 CMI response on Day 0, Day 21, and Day 42 measured by IFN- γ ELISpot will be compared between treatment groups and timepoints. The Wilcoxon Rank Sum Test, also known as the Mann-Whitney Wilcoxon Test, will be used to estimate the difference in response between treatment groups, along with the corresponding 95% CI for the median and p-value.

Since the response between timepoints are paired data, the Wilcoxon Signed Rank Test will be used to estimate the difference in response between timepoints, along with the corresponding 95% CI for the median and p-value.

Scatter plot of the number of T cells expressing IFN- γ will be created.

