**Figure 1 Study Flow**

5.3 Rationale for Study Design and Treatment Regimens

5.3.1 Randomization

Group 1 (3.75 µg of MT-2766) and Group 2 (placebo) will be randomized. Age (< 65 and ≥ 65) will be used as stratification factors. On the other hand, Group 3 (1.875 µg of MT-2766) will be not randomized.

With regards to Group 1 and 2, randomization will be used to minimize bias in the assignment of subjects to two treatment groups, to increase the likelihood that known and unknown subject attributes (e.g. demographic and baseline characteristics) are evenly balanced across treatment groups and to enhance the validity of statistical comparisons across treatment groups within each Study Population. On the other hands, Group 3 will be not randomized because of its exploratory purpose.

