5.4 Treatment Allocation and Blinding

5.4.1 Randomization

In the study, subjects in Group 1 and 2 will be randomized 4:1 to receive the 3.75 µg of MT-2766 and placebo. Eligible subjects will be randomized at the Day 0 visit using the interactive web response system (IWRS). Age (< 65 and ≥ 65) will be used as stratification factors.

No subjects will be randomized into the study more than once.

Subjects will be enrolled into treatment groups in the study based on a computer-generated randomization schedule prepared under the supervision of MTPC before the study. The details of treatment allocation will be specified in a separate procedure.

The treatment will be recorded along with a unique subject number for each subject.

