11.2.1 Immunogenicity Endpoints

See Section 2.2.1, 2.2.2 and 2.2.3.

Point estimates and 95 %CI will be calculated for all immunogenicity endpoints and responses

for the treatment groups will be compared using descriptive statistics.

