6.2 Statistical Tests

Unless otherwise specified, all formal statistical tests will be done at two-sided significance level of 0.05. Point estimates will be accompanied with two-sided 95% CIs where applicable.

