8.2.2 Secondary Immunogenicity Endpoints

8.2.2.1 Nab response against the SARS-CoV-2 virus

The following analyses for the Nab assay will be performed:

- GMT (Day 128 and Day 201): The point estimates and the corresponding two-sided 95 % CI by treatment group will be calculated.
- SC rate (Day 128 and Day 201): The point estimates and the corresponding two-sided 95 % CI for subjects achieving SC by treatment group will be calculated.
- GMFR: the geometric mean of the ratio of GMTs (Day 128/Day 0, Day 201/Day 0) will be calculated.

The same methodology as in section 8.2.1.1 will be used.

8.2.2.2 Specific Th1 CMI response against the SARS-CoV-2 virus measured by IFN- γ ELISpot

The specific Th1 CMI response induced on Day 201 will be analyzed according to the same methodology as in section 8.2.1.2.

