8.2.2.4 Specific antibody response against the SARS-CoV-2 virus by the total IgG levels

The GMT will be calculated on Day 0, Day 21, Day 42 and Day 201 as well as the GMFR (Day 21/Day 0, Day 42/Day 0, Day 201/Day 0). SC rate will be calculated on Day 21, Day 42 and Day 201.

GMT will be compared between treatment groups using the analysis of variance (ANOVA) model.

For SC rate, Fisher's exact test will be used to compare between the treatment groups, along with exact Clopper-Pearson 95% CI.

GMFR will be compared using the ANCOVA model. The GMFR will be derived by using ANCOVA to model the difference in the log of the titer values between Day 21 and Day 0, between Day 42 and Day 0, between Day 201 and Day 0 with treatment group as main effect and log-transformed baseline titer as covariate.

The RCD curve will be plotted.

8.2.3 Specific CMI response against the SARS-CoV-2 virus measured by the percentage of CD4+ T cells expressing functional markers

The CMI response on Day 0, Day 21 and Day 42 measured by the percentage of T cells expressing functional markers, using flow cytometry will be compared between treatment groups and timepoints. The Wilcoxon Rank Sum Test will be used to estimate the difference in response between treatment groups, along with the corresponding 95% CI for the median.

The Wilcoxon Signed Rank Test will be used to estimate the difference in response between timepoints, along with the corresponding 95% CI for the median.

Parameters
CD4+CD8- > IL2+ percent of CD4, CD4+CD8- > IL4+ percent of CD4, CD154+ > IFN_TNF_IL2_Poly percent of CD4, CD4+CD8- > IFN_TNF_IL2_Poly percent of CD4

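### Randomisation is stratified by age (<65, ≥65), but the GMFR ANCOVA leaves age out and the GMT ANOVA text names no age term: a small loss of precision at Days 21 and 42, and possible age imbalance later

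*SAP*

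**What the plan says.** Protocol 5.4.1, for the 4:1 randomisation of Groups 1 and 2: "Age (< 65 and ≥ 65) will be used as stratification factors". Protocol 5.3.1 gives one purpose of randomisation as "to enhance the validity of statistical comparisons across treatment groups within each Study Population".

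The SAP models are:

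- Nab GMFR (SAP 8.2.1.1): ANCOVA "with treatment group as main effect and log-transformed baseline titer as covariate".
- Nab GMT (SAP 8.2.1.1): "GMT will be compared between treatment groups using the analysis of variance (ANOVA) model". A placeholder for sample SAS code follows, but the code is not in the text available for review.
- Nab at Days 128 and 201 (SAP 8.2.2.1): "The same methodology as in section 8.2.1.1 will be used".
- IgG (SAP 8.2.2.4): the same ANOVA for GMT, and a GMFR ANCOVA whose terms end "between Day 201 and Day 0 with treatment group as main effect and log-transformed baseline titer as covariate".

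In the SAP's analysis text the <65/≥65 split appears only as a baseline characteristic (8.1.2). Protocol 14.4.2 also gives the GMFR model without age, so the two documents agree. Neither gives a reason.

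On the status of the comparison, Protocol 11.2.1 says that responses "for the treatment groups will be compared using descriptive statistics", whereas SAP 6.2 says "all formal statistical tests will be done at two-sided significance level of 0.05". SAP 1 states that the SAP prevails over the protocol on statistical detail.

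**The concern.** Stratified allocation removes most of the chance imbalance in age between the arms, so the true sampling error of the contrast no longer contains the age component. A model without age does not know this. It leaves the between-stratum variance in the residual, and the reported standard error is too large whenever age predicts titre. Because the SAP attaches two-sided 0.05 tests and 95% intervals to these contrasts, that standard error is used. Nab GMT and GMFR at Days 21 and 42 are primary endpoints.

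The later visits raise a second question. Protocol 5.5 recommends public vaccination to Group 2 after key open, and subjects who take it are withdrawn. If uptake depends on age, the balance set up at randomisation may not survive to Days 128 and 201.

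Only the between-group GMT and GMFR contrasts are affected. The per-arm GMT intervals, the Clopper-Pearson intervals and the Fisher and Wilcoxon tests are not at issue here.

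**Working it through.** **Inputs from the documents.** 125 subjects at 4:1, which gives 125 × 4/5 = 100 and 125/5 = 25; one stratification factor with two levels; two-sided α = 0.05. The sample size has no power basis (SAP 3.4), so there is no plan figure to reproduce.

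**Assumed inputs** (not in the documents): share p aged ≥65 of 20–40%; within-stratum SD of 0.45 or 0.6 log10; age effect of 1.5-, 2- or 3-fold; allocation balanced within strata, simulated as blocks of 5. Protocol 5.4.1 leaves the allocation details to a separate procedure.

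**Step 1: full, balanced sample; age acts in both arms; equal SDs.** With d = log10(fold)/SD, the model standard error without age is too large by r = √(1 + p(1−p)d²). Adding age narrows the interval by 1 − 1/r. The type I error without age is 2{1 − Φ(1.96 r)}.

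Example: SD 0.45, p = 0.3, 2-fold. d = 0.301/0.45 = 0.669; r = √(1 + 0.21 × 0.4475) = 1.046; narrowing 4.4%; type I error 2{1 − Φ(2.050)} = 4.0%.

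| p, fold | SD 0.45: narrowing | SD 0.45: type I error | SD 0.6: narrowing | SD 0.6: type I error |
|---|---|---|---|---|
| 0.2, 1.5 | 1.2% | 4.7% | 0.7% | 4.8% |
| 0.3, 2 | 4.4% | 4.0% | 2.5% | 4.4% |
| 0.4, 2 | 5.0% | 3.9% | 2.9% | 4.4% |
| 0.4, 3 | 11.3% | 2.7% | 6.8% | 3.5% |

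Simulation agrees with the narrowing to about 0.1 percentage point. In a separate set of simulations, type I error without age was 4.6% (p = 0.2, d = 0.5) and 3.2% (p = 0.3, d = 1.0), and 5.1% and 4.8% with age. When allocation was not stratified, the analysis without age showed no conservatism (5.1–5.4%), so the effect comes from the stratification.

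**Step 2: age acts only in vaccinees.** With vaccine SD 0.45 and placebo SD 0.1, the narrowing for the same four cases is about 1%, 3.4%, 3.9% and 8.8%.

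**Step 3: age balance lost by withdrawal.** Illustration: 90 vaccine and 10 placebo subjects remain, with 40% and 10% aged ≥65; SD 0.45; titres of older subjects halved in both arms; no vaccine effect.

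- Shift in the unadjusted contrast: −0.301 × (0.40 − 0.10) = −0.090 log10, a factor of 0.81.
- True SE: 0.45 × √(1/90 + 1/10) = 0.150.
- Model variance: 0.2025 + 0.0906 × (90 × 0.24 + 10 × 0.09)/100 = 0.2229. Model SE: √0.2229 × 0.333 = 0.157.
- Critical value in true-SE units: 1.984 × 0.157/0.150 = 2.08. Shift: 0.090/0.150 = 0.60.
- Type I error: Φ(−1.48) + Φ(−2.68) = 0.069 + 0.004, about 7%. With age in the model it is about 5%.

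Had both arms kept 40% aged ≥65, the figure without age would be just under 4%. Exchanging the two age shares changes the sign of the shift.

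**Step 4: cost of the term.** If age has no effect, the lost degree of freedom widens the interval by about 0.01%. Older placebo subjects number about 3–7 at a 20% share and 8–12 at 40% (5th–95th percentile).

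**The case against.** The strongest reply is that the analysis without age is valid, prespecified and consistent between protocol and SAP. The trial has no power calculation and no success criterion, and Protocol 11.2.1 calls the comparison descriptive. That stands as to severity: this is a question of efficiency. It does not remove the point, because the SAP does set formal tests and the improvement costs almost nothing.

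A second reply is that subjects enter without prior infection or COVID-19 vaccination, so placebo titres may sit near the assay floor, where age has little to act on. This also stands. Step 2 gives smaller gains, and the bias in Step 3 from placebo withdrawal alone needs age to shift placebo titres too. Unequal variance from placebo titres at the floor is a separate and larger issue, which an age term does not solve.

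A third is that the sample code for the ANOVA is not visible and may already contain age. Agreed: for the GMT the point concerns the text only.

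A reader might infer that ignoring the stratification factor inflates the type I error of the primary comparisons. It does not: with balance kept, the error moves the other way. A reader might equally infer that the contrasts are conservative at every visit. That is not supported either, because Step 3 shows that it depends on age balance in the analysed sample.

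**Conclusion.** The point holds as a minor one. The omission is firm for the GMFR ANCOVA (Nab and IgG) and is a matter of wording for the GMT ANOVA.

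At Days 21 and 42, if age predicts titre and allocation is balanced within strata, the contrasts are slightly conservative: about 1–5% in interval width for a 1.5- to 2-fold age effect at SD 0.45, and about 0.7–3% at SD 0.6. Only an age effect as large as 3-fold takes this to 7–11%. At Days 128 and 201 the direction cannot be stated in advance. The 7% in Step 3 shows what age-dependent withdrawal could do; it is not a forecast, since the documents give no withdrawal pattern.

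The share aged ≥65, the SD, the age effect and the balance within strata are all assumed. The calculations are for the ANOVA contrast. They carry over to the GMFR ANCOVA if baseline titres vary little, which is plausible in subjects screened as SARS-CoV-2 negative. Nothing here suggests that the vaccine-versus-placebo conclusion would change.

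**What to change.** Add the randomisation age stratum (<65, ≥65) as a factor to the GMFR ANCOVA for Nab and IgG, and to the GMT ANOVA if its code does not already contain it.

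Timing matters. SAP 4.1 and 4.2 provide for an interim lock and analysis of data up to Day 42, and SAP 10 shows that the current text was written after the study was discontinued. Where Day 21/42 results were already unblinded, keep the planned results as they are and report the age-adjusted ones as an additional analysis, labelled and explained as Protocol 14.5 requires for changes after data lock.

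The cost is one class term and one degree of freedom per model, on a variable already collected. The drawback is sparse older-placebo cells, probably sparser still at Days 128 and 201; the number of subjects per arm and stratum should be shown beside the adjusted estimates.
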